5. STUDY INTERVENTIONS

5.1 Interventions, Administration, and Duration

At each ED site, acupuncture intervention will be provided by one of two licensed acupuncturists with the option of a third backup acupuncturist for flexibility in coverage. Since there will be various pain presentations (musculoskeletal: back, neck, limb pain, abdominal or flank pain, headache etc.), the acupuncture intervention will adhere to the manualized protocol (developed in year 1 of the grant). The manualized protocol promotes standardization as well as flexibility based on the acupuncturist's assessment of the patient's presentation within a predetermined framework and contextual considerations such as accessibility of various parts of a patient's body. Receiving acupuncture will not affect the patient's usual care in that any medications (including opioid medications) will be administered as usual, as needed, after collection of 'post' scores and under the direction of the patient's emergency care provider team.

Consistent with pragmatic trials,³⁹ we have chosen to compare Acupuncture therapy to Usual Care rather than to a sham acupuncture treatment. At this stage of investigating acupuncture in the ED, we agree with the current consensus view in the acupuncture research community that research designs such as those used to study new pharmaceutical treatments are not adequate in the study of effectiveness for therapies like acupuncture.⁷⁶ Further rationale for this choice stems from the consensus of the DoD/NIH Acupuncture for the Treatment of Acute Pain Workshop.⁶⁷ After two days of meeting with experts in statistics, acute pain and acupuncture, there was agreement from DoD, VA and civilian experts that design of acupuncture studies should compare acupuncture plus usual care to usual care alone. Our proposal is also consistent with the NIH Collaboratory recommendation for pragmatic trials.⁴⁰

The study acupuncturists will adhere to the following approach:

- The acupuncture therapy intervention will be based on staging an interview/conversation, palpation, and selection of points or methods for treatment based on presenting factors. The acupuncturist will record the specific acupuncture points, the number of needles used, length of needle retention if applicable, length of session time, any limitations on session time, points used for extended auricular therapy, if applicable, and response from point stimulation based on parameters of the responsive manualization protocol (Aim 1). A consensus of common points utilized for acute pain in the ED can be expected with additional points at the discretion of the acupuncturist treating the patient. Hand rotation and perturbation of needles to de qi status is allowed; electrical stimulation or moxibustion are not included in this trial. Needle retention time can vary and may range from 5-40 minutes, but commonly will be 15-30 minutes. Total session time may vary due to the patients' tolerance of the treatment, acupuncturists' assessment of the patient or workflow consideration of the ED, such as a patient needing to leave the room for imaging to be performed.
- Sterile, single-use non-coated acupuncture needles will be used for this study. Needles in sizes of .22x13mm, .25x25mm, .25x40mm, and .30x40mm, and will be available. The choice of needle size used will be left to the discretion of the acupuncturists treating the patient.
- Treatment regimen: Each patient randomized to the Acupuncture arm will be provided no more than one treatment per admission to the ED. Due to workflow considerations of the ED of this pragmatic RCT, it is possible that some patients randomized to the Acupuncture arm of the study will not receive acupuncture.
- Extended therapy pressure: Ear seeds will be retained on auricular acupuncture points in order to "extend the treatment benefit after ED care". We will use vaccaria seed with latex adhesive, and have a non-latex alternative for patients with latex allergy. Use and location of the ear seeds will be at the discretion of the acupuncturist. Patients will keep them on the ears after discharge from the ED, and are directed to leave them on until they fall off or remove them if they become uncomfortable. The ear seeds can be peeled off and thrown into the trash

- Acupuncturists will attempt to provide the acupuncture intervention as close to the beginning of the patient's ED visit as possible, after evaluation by the attending ED provider. The rationale for this decision is to help evaluate the use of acupuncture as a first line intervention for pain relief.
- Acupuncturists will be nationally board certified and remain current with the National Commission for the Certification of Acupuncture and Oriental Medicine (NCCAOM) which includes passing of infection control standards exam; they will also have a valid and current state acupuncture license.
- Acupuncturists will provide the participant with the Acupuncture Post Care information sheet (attached to the IRB smart application) at the completion of the acupuncture treatment. This sheet has information about the ear seeds and general after care instructions.

Usual Care: Patients assigned to the Usual Care arm will receive care and treatment for pain and any other symptoms or conditions as would usually be provided in the ED, in accordance with the relevant pain management and care policy at each participating ED. Furthermore, we have designed our study (see Figure 1) so that the medications provided to Usual Care patients will have enough time to take effect serving as a more pragmatic control to the Acupuncture arm than sham acupuncture.

Based on our successful prior experience with our observational study and RCT, the likelihood of adverse physical, psychological, social, and legal risks is expected to be very small. Acupuncture carries very slight risks for

- Bleeding,
- Bruising,
- Fainting (acushock)
- Needling pain

In the event a patient experiences an adverse event (AE), they will be treated by providers in the site ED and will have access to emergency response equipment as necessary.

Acupuncture involves inserting thin, sterile needles in the skin. The needles are not inserted into the skin very far. Sometimes the needles cause slight discomfort or minor bleeding. Any acupuncturist who provides treatments in this study will be licensed by the state in which they practice.

Monitoring of the study for AEs will be continuous throughout the study. In the event of an AE or SAE, it will be reported to the UH IRB in compliance with UH IRB standards.

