Patient qualitative interviews will be conducted via the audio-only function of a HIPAA-compliant commercial tele-health platform: (e.g. Zoom Health Professional or Doxy.me) or over the phone and will be recorded and transcribed. Provider and Study Staff interviews will happen in person in a private room or via the audio-only function of a HIPAA-compliant commercial tele-health platform: (e.g. Zoom Health Professional or Doxy.me) or over the phone. Study staff at the Einstein Coordinating Center conducting the interviews via secure online platform will be in a private room when interviewing the participants.

Approximate duration of enrollment period and follow-up

Patients will be enrolled for approximately 4 weeks. Each site will enroll for 6-9 months, and enrollment at the last site will be completed approximately 12 months after enrollment at the first site begins.

Description of intervention and administration

Intervention Arms

Acupuncture therapy. At each ED recruiting site, acupuncture intervention will be provided by one of two licensed acupuncturists with the option of a third backup acupuncturist for flexibility in coverage. Since there will be various pain presentations (musculoskeletal: back, neck, limb pain, abdominal or flank pain, headache etc), the acupuncture intervention will adhere to the responsive manualized protocol (developed in Year 1 of the grant). The responsive manualized protocol promotes standardization as well as flexibility based on the acupuncturist's assessment of a patient's presentation within a predetermined framework and contextual considerations such as accessibility of various parts of a patient's body. Receiving acupuncture will not affect the patient's usual care in that any medications (including opioid medications) will be administered as usual, as clinically needed, after collection of 'post' scores and under the direction of the patient's emergency care provider team.

Consistent with pragmatic trials,³⁹ we have chosen to compare Acupuncture therapy to Usual Care rather than to a sham acupuncture treatment. At this stage of investigating acupuncture in the ED, we agree with the current consensus view in the acupuncture research community that research designs such as those used to study new pharmaceutical treatments are not adequate in the study of

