5.3.3 Prohibited Interventions

For those in the treatment group, pain medications will be delayed until after completion of acupuncture intervention.

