6.2 Description of Evaluations

6.2.1 Screening Evaluation

At each ED, the Study Coordinator (SC) or Research Assistant (SC) and acupuncturist will work as a team, staffing an average 2.5, 4-6 hour recruitment/intervention sessions per week, varying the times

and days across sites as this may influence adoption. As in Figure 1, after the ED RN conducts the initial triage activity, the SC or RA (“study staff”) will identify and conduct initial eligibility pre-screening in the in the ED triage unit. The patient will then be roomed and seen by the ED clinical provider. If the ED provider determines that patient does not have a clinical condition prohibiting study participation, s/he will sign a study approval form (see below). The study staff will then approach the patient for study participation.

Provider sign off

Acupuncture in the Emergency Department for Pain Management (ACUITY)

If the patient is randomized to the acupuncture arm, please withhold pain and anxiety medications until after the acupuncture session.

The study coordinator will inform you what arm they are assigned to and when their session has ended.

In order for this patient to be eligible to participate in the "Acupuncture in the ED" study, please verify you have examined the patient and believe to the best of your knowledge, at this time, that the patient does not have the following conditions:

Critical status / Trauma
 Bone fracture
 Joint dislocation
 Migraine
 Psychological / psychiatric concern
 Clinical judgement / Other:

If you deem the patient eligible for the study, the patient will be randomized to acupuncture or usual care.

Patient can continue in study
 Patient is excluded from study

Sign: _____

Consenting Procedure

We have requested a partial HIPAA waiver for prescreening. Therefore, patients will only be consented once the screening process is over and eligibility is confirmed.

The consent process will occur after the patient has gone through the triage process and been assigned to a room within the ED. The consent process will be conducted by dedicated research staff (SC or RA) that have been trained in obtaining informed consent and who have current Human Subjects Protection and Good Clinical Practice certifications. The status and location of the patient will be monitored by

research staff using the EHR to ensure the patient is approached at an appropriate time.

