6.2.4 Follow-up Visits

Post Treatment Assessment

- Post-Treatment Pain Assessment (Post) using a 0-10 NRS will be collected within 60 minutes (+/- 15 minutes) of the Pre-Treatment score, thus including the acupuncture and usual care periods. Based on pharmacokinetics of the most common pain medications used in emergency care one hour is the maximum time to effectiveness for any pain medication currently administered in most EDs.
- Anxiety scores using a 0-10 NRS will be collected at the same time as pain intensity.
- Satisfaction and will be measured through brief questions. All participants will be asked to answer:
 - "How satisfied are you with how your pain was managed during your ED visit" on the 5-point Likert scale.

- “Overall how satisfied are you with your treatment during your ED visit?” on the same Likert Scale. CI across sites as well as across patient groups such as different presenting complaints and patient demographics.

ED Discharge Assessment

ED Discharge Assessment (ED Discharge) will be obtained within 15 minutes of patients' discharge from the ED, for both acupuncture and usual care patients. If the study staff's shift has ended and it has been longer than 15 minutes since collecting post-treatment scores, study staff will collect discharge scores from the participant and leave for the day. Discharge scores will not be attempted to be collected if the participant is discharged within 15 minutes of when post treatment scores were collected. This will not be considered missing data.

- Pain Assessment (Post) using a 0-10 NRS
- Anxiety scores using a 0-10 NRS
- Satisfaction and will be measured through brief questions. All participants will be asked to answer;
 - “How satisfied are you with how your pain was managed during your ED visit” on the 5-point Likert scale.
 - “Overall how satisfied are you with your treatment during your ED visit?” on the same Likert Scale. CI across sites as well as across patient groups such as different presenting complaints and patient demographics.
- ED Impact and will be measured through a brief question given to Acupuncture patients only at ED discharge, participants will be asked to answer;
 - “Please rate the impact of acupuncture on your ED visit today.” on the 5-point Likert scale.
- All pain medications utilized in the ED will be obtained from the EHR after patient discharge.

One Week Follow-Up Assessment Visit

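### Sections 3 and 5.1 hold acupuncture-arm medication until the Post score is taken, but section 5.3.3 and the provider sign-off form release it at session end, which can come before Post

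*Combined protocol and SAP*

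**What the plan says.** Two places set the release point at the Post score. Section 5.1 states that "any medications (including opioid medications) will be administered as usual, as needed, after collection of 'post' scores". Section 3 (Intervention Arms) says that medications "will be administered as usual, as clinically needed, after collection of 'post' scores".

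Two places set it at the end of the session. Section 5.3.3 says that, for the treatment group, "pain medications will be delayed until after completion of acupuncture intervention". The provider sign-off form in section 6.2.1 asks: "please withhold pain and anxiety medications until after the acupuncture session". The form also tells the provider what signal to expect: "The study coordinator will inform you what arm they are assigned to and when their session has ended". Neither 5.3.3 nor the form mentions the Post score.

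Section 6.2.4 ties Post to the Pre score: it "will be collected within 60 minutes (+/- 15 minutes) of the Pre-Treatment score". For anxiety, it adds: "Anxiety scores using a 0-10 NRS will be collected at the same time as pain intensity".

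Section 5.3.1 separately lets the responsible clinician prescribe whatever is needed for a participant's health, in either arm.

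**The concern.** The person who prescribes is given the earlier of two release points. A patient medicated after the session but before Post complies with 5.3.3 and the form, yet breaches 5.1. Deviations must be logged and graded at each site (section 10.3.3), so the three sites could classify the same event differently.

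What is at stake is how the acupuncture-arm Pre-to-Post change is read. Section 5.1 places acupuncture early in the visit to help evaluate it as a first-line option for pain. A Post score taken after an analgesic or anxiolytic mixes the two treatments. Section 6.2.4 treats one hour as the longest time common ED pain medications need to take effect, so a drug given less than an hour before Post could still influence it. The study's primary objective is to refine procedures for a later full trial, and an unclear release rule is a procedure that trial could inherit.

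**Working it through.** The plan gives no figure for this gap, so there is none to reproduce. The check compares the rules and then works out what timing they permit.

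**Step 1: rules side by side.**

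| Source | Release point | Mentions Post? |
|---|---|---|
| Section 3 | after Post is collected | yes |
| Section 5.1 | after Post is collected | yes |
| Section 5.3.3 | after acupuncture is complete | no |
| Sign-off form (6.2.1) | after the session; coordinator reports its end | no |

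**Step 2: inputs, in minutes from Pre.**

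- Post window (6.2.4): 60 - 15 = 45 to 60 + 15 = 75.
- Delay d from Pre to session start: above 0, because randomization follows baseline collection (6.2.2; Appendix B, PRE form). Its length is not given. I assume 5 and 15.
- Session length L: not given for this trial. Section 5.1 gives only needle retention: "Needle retention time can vary and may range from 5-40 minutes, but commonly will be 15-30 minutes". Sessions also include interview and palpation, so retention understates L. The pilot's session was about 45 minutes (section 2.2). I use L = 45, and L = 30 and 20 as assumptions.

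**Step 3: gap between release under the form and Post.**

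Gap = max(0, Post time - (d + L)).

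| L | d | Post at 45 | Post at 60 | Post at 75 |
|---|---|---|---|---|
| 45 | 5 | 0 | 60 - 50 = 10 | 25 |
| 45 | 15 | 0 | 60 - 60 = 0 | 15 |
| 30 | 5 | 10 | 60 - 35 = 25 | 40 |
| 30 | 15 | 0 | 60 - 45 = 15 | 30 |
| 20 | 5 | 20 | 60 - 25 = 35 | 50 |
| 20 | 15 | 10 | 60 - 35 = 25 | 40 |

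Starting the session at Pre itself (d = 0) adds 5 minutes to every non-zero d = 5 entry. If Post is taken at session end, the gap is 0 for any d and L.

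**Step 4: what the gap measures.** It runs from permitted release to Post. A drug must still be ordered and given after release, so the time from administration to Post is shorter, and may be nil.

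**The case against.** The strongest reply is that every rule can be obeyed at once. The wording in 5.3.3 sets a minimum delay, and sections 3 and 5.1 are merely stricter. Study staff both collect the scores and notify the provider, so collecting Post first satisfies all four places. In the pilot, session end triggered Post, and section 9.2 describes the goal as testing the feasibility of the pilot's procedures. Figure 1, the Manual of Procedures and the ED visit checklist are not visible here and may fix that order.

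Part of this stands: the rules are compatible in practice if Post comes first, and the gap is then zero. But no visible text requires that order, and a general reference to the pilot's procedures does not supply it. The form would still name session end, and the Manual is not on the training list for ED physicians who do not recruit (section 10.3.1).

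A second reply is that the comparison is acupuncture plus usual care against usual care alone, so medication in the acupuncture arm belongs to the contrast. That is fair for the visit as a whole. For the Post score, however, sections 3 and 5.1 explicitly put medication afterwards.

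A reader might also infer two further errors: 5.3.3 names only pain medication while the form adds anxiety medication, and nothing says when the hold ends if no session is given. These are better read as missing detail. Section 5.1 already covers any medication, the prescriber's own form names both classes, and 5.3.1 lets the clinician treat on clinical need.

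**Conclusion.** The conflict stands in the current text. A provider who follows the form can medicate before Post, contrary to sections 3 and 5.1. The consequence is limited to the descriptive acupuncture-arm Pre-to-Post change in pain and anxiety.

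Only the possibility is established. The documents do not show how often medication precedes Post or how far it would shift the scores. The minutes above rest on assumed delays and, apart from the pilot's 45, assumed session lengths. At the one documented session length, with Post at 60 minutes and d of 5 to 15, the gap is 0 to 10 minutes. The 50-minute entry combines the shortest assumed session, the shorter assumed delay and the latest Post, and should not be read as typical.

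Section 9.5 calls pain change a primary outcome and the 6.1 table lists Post pain and anxiety as primary assessments, so a reader might infer that the trial's main result is compromised. The documents do not support that. Sections 3 and 9.5.1 make recruitment and retention primary, neither depends on the release rule, and no powered test in this study uses the Post score.

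**What to change.** - In 5.3.3 and on the sign-off form, make the release cue completion of the Post score. Have the coordinator notify the provider once Post is done, not when the session ends.
- Keep Post at the same target time from Pre in both arms. Moving it to session end in the acupuncture arm alone would close the gap but could create a between-arm difference in measurement time.
- State that rescue under 5.3.1 remains available at any time.
- From the ED pain-medication data already planned from the EHR (6.2.4, 10.2), report how many acupuncture-arm patients received pain medication before Post, beside the Pre-to-Post summaries. This needs administration times; the visible text does not say whether the extract includes them, so confirm that.

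The cost is a few words in one section and one form, plus one reported count. The downside is that some patients wait longer for non-rescue medication than the form now allows. With Post held at 60 minutes, the added wait equals the gap in the table: 0 to 10 minutes at L = 45, 15 to 25 at L = 30 and 25 to 35 at L = 20, under the same assumptions. Measured against section 5.1 as written there is no added wait, because 5.1 already holds medication until Post.

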5.2 Handling of Study Interventions

Sterile, single-use non-coated acupuncture needles will be used for this study. Needle sizes of .22x13mm, .25x25mm, .25x40mm, and .30x40mm will be available. The choice of needle size used will be left to the discretion of the acupuncturists treating the patient. Ear seeds will be retained on auricular acupuncture points in order to "extend the treatment benefit after ED care". We will use vaccaria seed with latex adhesive, and have a non-latex alternative for patients with latex allergy. Use and location of the ear seeds will be at the discretion of the acupuncturist.

5.3 Concomitant Interventions

5.3.1 Allowed Interventions

As the study is taking place in the active clinical ED, the responsible ED clinician will have the ability to prescribe any medications or interventions to maintain the health of a participant regardless of the treatment assignment of the participant.

5.3.2 Required Interventions

Acupuncture is required for those in the treatment group

5.3.3 Prohibited Interventions

For those in the treatment group, pain medications will be delayed until after completion of acupuncture intervention.

5.4 Adherence Assessment

N/A

6. STUDY PROCEDURES

6.1 Schedule of Evaluations

Randomized Control Trial

Treatment Variables. Main patient reported treatment outcomes (PROs) include pain intensity and anxiety. The use of self-reported pain ratings to assess pain is standard clinical practice.^{68,69} Although self-report of pain intensity is subjective, a reliable physiological measure to quantify pain has not been identified.⁷⁰ These measures will be collected via tablet computer in the PHI-approved data collection tool (REDCap). A similar process was used in [name]'s pilot RCT. The study staff will hand the patient a tablet for confidential self-administration. Once the patient completes the questionnaires, the answers will be masked so the research staff will not have access to the scores. To keep research staff blinded to scores, the data collection tool will be designed so that the study staff will only be able to determine that valid pain and anxiety scores were entered by the patient. In other words, staff will not have access to the actual pain or anxiety scores until the statistician conducts the final analysis. Data will be collected as shown in Table below.

Treatment Variables	Measure/Source	Data Collection Time point			
		Pre-Treatment	Post-Treatment	ED Discharge	1-week and 4-week Follow-up
Primary Assessment (* and bold)					
Pain Intensity	Numeric Rating Scale, 0-10^{58,59}	X	X*	X*	X^
Anxiety	Numeric Rating Scale, 0-10^{58,59}	X	X*	X*	X^
Secondary Assessment (^ and italic)					
All pain medications in the ED	EHR			X^	
Pain medication/opioid use	Self-report				X^
Baseline variables of interest					
Demographics	EHR data and self-report	X			
Current Medications		X			
Opioid use – last 30 days	Self-report	X			
Previous acupuncture use		X			

ED visits in last year	X
Other variables of interest	
Expectancy	Self-report
Satisfaction questions	X
ED impact (ACUPUNCTURE ONLY)	X

Qualitative Interviews

Patient Interview Guide

U01 Acupuncture Study Patient Interview Topic Guide Preliminary Draft 10-23-20
1. Pain narrative—history, cause, impact, course, treatment experiences Possible prompts: i. Tell me about your pain condition... ii. How long have you had it? iii. What causes it? iv. How does it impact you? v. Tell me about your pain condition over time—wax/wane? Always the same? Exacerbating issues? vi. Tell me about your treatment and management experiences
2. Attitudes/perception of acupuncture—previous treatment history, beliefs Possible prompts i. What was your experience of acupuncture before your (index) ED visit? ii. What were your views of acupuncture? iii. Did your views change after your ED acupuncture visit?
3. Index ER Visit—the decision to visit the ED, previous ED visits, description of the visit Possible Prompts i. Why did you decide to go to the ER? Have you visited the ER before? For the same problem? Tell me about it. ii. Tell me about your visit? What was it like in the ER during that visit? Tell me about it.
4. Acupuncture Study in the ED—the decision to participate Possible Prompts i. Why did you decide to participate in the Acupuncture study? Tell me about that.
5. Experience of acupuncture in the ED—index visit Possible Prompts i. Describe your experience with acupuncture during that visit—timing, location, length of treatment, behavior of the acupuncturist, other ED staff ii. Did it impact your pain? Right away or after a while? Tell me about it? iii. What surprised you about this experience? iv. Are there ways it could have been improved? v. Did you receive other treatments? Tell me about that.
6. Post treatment experiences Possible Prompts i. Tell me about what happened after your visit? Where did you go? What did you do? ii. Tell me about your pain. Was it better after your visit? Did it get better over time? Is it better now? Tell me about it iii. What do you attribute your improvement/lack of improvement to? iv. If the acupuncture helped, how or why did it help? v. Are you or would you seek further acupuncture treatments? vi. Did other treatments you received also help? vii. Were there treatments you did not receive that would have helped?
7. Pain in the future i. How do you see your pain in the future? ii. Would you seek out ED treatment again if you experienced the same pain? Why or why not? iii. Would you seek out acupuncture, in the ED or outside the ED? Why or why not?

Provider Interview Guide

U01 Acupuncture Study
Provider Interview Topic Guide
Preliminary Draft 10-23-20
Preliminary: age, gender, profession, specialty

1. Treating pain in the ER—experiences, perceptions, challenges

Possible prompts:

- i. Tell me about treating pain in the ER
- ii. What are some of the challenges?
- iii. What are typical cases?
- iv. How do you usually treat them?
- v. Is treating pain in the ER challenging?
- vi. What would make your job of treating pain in the ER easier?

2. Attitudes/perception of acupuncture—previous treatment history, beliefs

Possible prompts:

- i. Can you describe your personal experiences with acupuncture, if any?
- ii. Can you describe your professional experiences with acupuncture, if any?
- 1. Is it helpful for patients?
- a. All patients? Some patients? Why does it work better/worse for some?
- iii. Overall, what were your view of acupuncture? Does it work? How do you think it works?

3. Acupuncture in the ER—initial perceptions of the research project

Possible Prompts

- i. What was your initial reaction to the idea of introducing acupuncture into the ER setting? What were some of the benefits you perceived? Challenges?
- ii. Now that the project is underway, have there been any surprises? Did the acupuncture work as well/as poorly as you expected?
- iii. What were some of the hiccups/issues that occurred with this research project?
- iv. What about the burden of the project?
- v. What is your view, now, of the value of inserting acupuncture in the ER?
- vi. After your experiences with our research project, what do you think about implementing acupuncture on an ongoing basis in the ER?
- vii. If yes:
 - 1. What would be some of the challenges? How would you overcome them?
 - 2. What would be the benefits?
- viii. If no:
 - 1. Why not? Tell me about that

Study Staff Interview Guide

ACUITY PROJECT Staff Interview Guide

Thank you for doing this interview with me. It will take about 15-30 minutes. This zoom interview will be recorded.

Overall, how did this project go in your setting?

- o What surprised you, in implementing this project?
- o What went well?
 - Were there resources and/or sources of support that made things go well?
- o How did project implementation change over time? Did things improve? Were there times when the project was easier or more difficult?
- o What were the biggest challenges?
- o In terms of coping with these challenges, what strategies did you use?
 - Did you learn/figure out new strategies/approaches as you went along? What were those?
 - What help or resources did you draw on to address these challenges?
 - What help or resources were missing that would have helped you better address these challenges?

Great. Now I'd like to run over a few of the issues that came up during our site visits. I'm going to ask you about issues you haven't addressed yet.

- Built environment (space/location)
- Staffing issues
- Red tape/IRB/Regulatory Binder
- Physician receptiveness
- Champion availability
- Patient receptiveness
- Recruitment issues
- Retention issues
- Training and communication from lead site
- Other

Given your overall experiences with the project so far, what do you think are the implications for sustainability/replication of the study interventions?

Do you think it would have been easier/more difficult to implement the study at a different site? What special features of your site made it easier or more difficult to implement the study?

Structured Observations

ACUITY FIELD NOTES TEMPLATE
 
NOTE: ONLY CONSENTED PATIENTS WILL BE OBSERVED DURING STUDY PROCEDURES. OBSERVERS WILL WEAR APPROPRIATE PPE AND MAINTAIN A SIX FOOT DISTANCE FROM STAFF AND PATIENTS AT ALL TIME
 
OBSERVER: DATE: SITE: TIME OF OBSERVATION: INITIAL DESCRIPTION—level of activity, noise, temperature, mood, in the ER:
 
Acupuncture Participants (Research staff, ED staff, and Participants)
 
1. PRESENTATION IN THE ED: The patient's initial presentation and interactions between patients and ED staff. Note patient verbal and nonverbal behaviors, tone of interactions, pain behaviors, etc.
 
Persons involved: Notes:
 
2. INITIAL INTERACTIONS BETWEEN RESEARCH AND ED STAFF: Study coordinator and ED staff interactions. Note staff response to request for participant enrollment.
 
Persons involved: Notes:
 
3. ENROLLMENT AND STUDY PROCEDURES: Initial approach, consent, randomization. Note patient verbal and nonverbal behaviors, pain behaviors, questions asked, tone of voice.
 
Persons involved: Notes:
	
1. THE ACUPUNCTURE SESSION—Note patient verbal and nonverbal behaviors, interactions between acupuncture provider and patient
 
Persons involved: Notes:
 
1. POST ACUPUNCTURE INTERACTIONS—Note patient verbal and nonverbal behaviors and interactions with staff, location of observation, pain behaviors, etc.
 
Persons involved: Notes:

---	---

Feasibility Survey

ACUITY Feasibility Survey

1. What is your sex assigned at birth?
 - a. Female
 - b. Male
 - c. Intersex
 - d. Decline to answer
2. What is your current gender identity?
 - a. Female
 - b. Male
 - c. Trans male/Trans man
 - d. Trans female/Trans woman
 - e. Genderqueer/Gender non-conforming
 - f. Different Identity [FREE TEXT]
 - g. Decline to answer
3. What is your ethnicity?
 - a. Hispanic or Latinx
 - b. Not Hispanic or Latinx
 - c. Decline to answer
4. What is your race? Check all that apply.
 - a. American Indian or Alaska Native
 - b. Asian
 - c. Black or African American
 - d. Native Hawaiian or other Pacific Islander
 - e. White
 - f. Other [FREE TEXT]
 - g. Decline to answer
5. What is your Age?
 - a. ____ years
6. How long have you worked in an ED?
 - a. ____ months
7. What is your occupation?
 - a. Nurse,
 - b. APP,
 - c. resident,
 - d. attending physician,
 - e. other if other [FREE TEXT]
8. Did you have any direct contact with the ACUITY study?
 - a. No
 - b. Yes
- 8a. if yes please briefly describe the specific contact you had with the ACUITY study or ACUITY staff [FREE TEXT]
9. Have you ever received acupuncture?
 - a. No
 - b. Yes

9a. IF yes, please do your best to recall about how many times you have received acupuncture

- a) 1 time
- b) 2-4 times
- c) 5-10 times
- d) 11-15 times
- e) 16 or more times

We have two questions about your opinion of acupuncture in general—as a treatment in the ED.

1. Do you view acupuncture in general as an appropriate intervention for the ED setting? (Likert scale (1-very appropriate—5-Very inappropriate)
2. Do you view acupuncture in general as helpful in managing patient pain in the ED? (Likert scale (1-Very helpful—5- Not at all helpful)

We also have two questions about your opinion of how the ACUITY research project was delivered in your ED.

[figure not shown]
1. Were you satisfied with how the ACUITY acupuncture intervention was delivered in your setting? (Likert scale (1-Very satisfied—5-Very dissatisfied)
2. Did the ACUITY project impose a burden on ED staff in your setting?
 - 1 – Not a burden
 - 2 – Somewhat of a burden
 - 3 – Moderate burden
 - 4 – Extreme burden

